### 2.2.4 Sample Size Determination

The study will enroll approximately 50 eligible subjects. Enrollment may be expanded up to a total of approximately 100 subjects to ensure that at least 8 treated and 4 placebo Phase 2a subjects are MRSA subjects and to account for additional subjects and cohorts that may be enrolled based on DRC review and Sponsor input based on emerging data. To ensure that at least 8 treated and 4 placebo Phase 2a subjects are MRSA subjects, no more than approximately 70 non-MRSA subjects will be enrolled without a protocol amendment.

The Phase 1b MAD safety cohorts will follow a standard 3 + 1 design for 2 cohorts (n = 4 for each cohort for a total of 8 subjects). However, additional cohorts (up to 3) may be added or existing cohorts expanded per recommendation of the DRC or Sponsor decision. The total sample size in Phase 1b may be increased up to a total of 20 subjects without a protocol amendment in consultation with the DRC.

Phase 2a will have an initial sample size of approximately n = 42 with a study drug to placebo allocation of 2:1 in order to enroll at least 38 subjects meeting the Microbiological Intent-to-Treat (MITT) Population criteria with the assumption that approximately 90% of randomized subjects will satisfy the MITT Population criteria. This will provide at least 80% power to detect a difference of 50% in the proportion of subjects in each treatment arm, with a 30% placebo portion meeting all conditions for Clinical Improvement or response at TOC for study drug (Day 12) in the MITT Population with a type 1 error rate of 0.05 (1-sided) using Fisher's exact test. Additional subjects may be included in Phase 2a after a protocol amendment.

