Late composite efficacy will be assessed programmatically based on the blood cultures tested by local microbiology laboratories per the definition in [section 2.3.2](#) at EOS. Proportion of subjects who experience late composite efficacy will be provided. Chi-square test p-value will be provided for the counts of subjects who experience late composite efficacy to compare AP-SA02 and placebo.

Microbiological failure or relapse will be assessed programmatically based on the blood cultures tested by local microbiology laboratories per the definition in section 2.3.2. Proportion of subjects who experience microbiological failure or relapse at TOC for study drug (Day 12), TOC for BAT (7 days [ $\pm 1$  day] after the end of BAT) and EOS (28 days after the end of BAT) will be provided.

If subjects have microbiological failure or relapse at TOC for study drug (Day 12) and negative blood cultures after Day 12, then subjects will not be included as microbiological failure or relapse at TOC for BAT (7 days [ $\pm 1$  day] after the end of BAT) or EOS (28 days after the end of BAT). If subjects have microbiological failure or relapse at TOC for BAT (7 days [ $\pm 1$  day] after the end of BAT) and negative blood cultures after TOC for BAT, then subjects will not be included as microbiological failure or relapse at EOS (28 days after the end of BAT). Chi-square test p-value will be provided for the counts of subjects who experience microbiological failure or relapse to compare AP-SA02 and placebo.

Time to death will be analyzed. Subject alive will be censored at the last date to be known alive.

$$\text{Time to death (days)} = \text{Censoring date/death date} - \text{date of first dose of study drug} + 1$$

The Kaplan-Meier method will be used to estimate the 25%, median and 75% times. The hazard ratio, 95% confidence interval (CI) of hazard ratio, and p-value from Cox regression model will be provided to compare AP-SA02 and placebo. Cox regression will include treatment (AP-SA02 and placebo) as factor.

Time to hospital discharge (and time to hospital discharge readiness) will analyzed. The subjects who will be in the hospital during the study will be censored at the date of last visit.

- Time to hospital discharge (days) = Censoring date/first hospital discharge date – date of first dose of study drug + 1
- Time to hospital discharge readiness (days) = Censoring date/first hospital discharge readiness date – date of first dose of study drug + 1

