## 7 PROGRAMMING SPECIFICATIONS

Analyses will be performed using SAS® version 9.3 or higher. Detailed Programming Specifications will be provided in a separate document.

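### The time-to-death endpoint is planned as Kaplan-Meier quartiles plus a Cox hazard ratio, which will often be uninformative with about 14 placebo subjects; a mortality difference with a confidence interval should be added

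*SAP*

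**What the plan says.** SAP 3.4.1 on mortality: "Time to death will be analyzed. Subject alive will be censored at the last date to be known alive". It continues: "The Kaplan-Meier method will be used to estimate the 25%, median and 75% times". A Cox model with treatment as the only factor then supplies the hazard ratio, its 95% CI and a p-value. The SAP does not say whether that p-value is Wald, score or likelihood ratio. It gives no rule for an arm without deaths. It asks for no mortality at a fixed day and no mortality difference. Death is also the only time-to-event endpoint without a planned Kaplan-Meier plot; SAP 3.4.1 and 3.6 list plots for NEWS2, focal signs, discharge, resolution of bacteremia and signs of bacteremia.

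SAP 3.4 applies the efficacy analyses to Phase 2a and also to Phase 1b, the Per Protocol MITT population, and the Phage Persistence and Clearance groups.

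Deaths appear elsewhere too. SAP 3.7.1 tabulates subjects with fatal adverse events by arm, with percentages and a chi-square p-value, and collects events through EOS. The Safety Population (SAP 3.2.5) consists of the same dosed subjects as the SAP's ITT population. Death counts as no response in Protocol Table 2, and survival at EOS is one part of the late composite. SAP 3.1.4 says there will be no formal testing.

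**The concern.** Quartile times and a Cox hazard ratio describe survival well when there are many events in both arms. Here the smaller arm has about 14 subjects in Phase 2a and about 2 in Phase 1b. With few deaths, the planned summaries for this endpoint may come out blank, infinite, or attached to a p-value that says nothing about the data. Death is the gravest outcome in a first-in-human trial, and its own analysis should give a readable estimate. What is at stake is the usefulness of that analysis and its consistency with the safety tables.

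**Working it through.** **Inputs.** SAP 2.2.4: "Phase 2a will have an initial sample size of approximately n = 42 with a study drug to placebo allocation of 2:1". So 42 × 2/3 = 28 on AP-SA02 and 42 × 1/3 = 14 on placebo. The SAP also assumes "approximately 90% of randomized subjects will satisfy the MITT Population criteria": 42 × 0.9 = 37.8, about 38, or roughly 25:13. Phase 1b as planned is two cohorts of 4 at 3:1, giving 6:2. No document states a mortality rate, so a range is assumed.

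**The plan's own figure.** SAP 2.2.4 states, for clinical response: "This will provide at least 80% power to detect a difference of 50% in the proportion of subjects in each treatment arm", "with a type 1 error rate of 0.05 (1-sided) using Fisher's exact test". Exact enumeration for 30% vs 80% at 25:13 gives 87.8%, so the stated bound is met. That figure does not bear on mortality.

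**Quartile times.** With complete follow-up, the 25% time needs at least 0.25 × 28 = 7 deaths on AP-SA02 and at least 0.25 × 14 = 3.5, that is 4, on placebo. The median needs 14 and 7. Below these counts there is nothing to report.

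**Chance of no deaths in an arm of n.** (1 − p)^n:

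| Assumed mortality | n = 14 | n = 2 (Phase 1b) |
|---|---|---|
| 5% | 0.95^14 = 49% | 0.95^2 = 90% |
| 10% | 0.90^14 = 23% | 0.90^2 = 81% |
| 20% | 0.80^14 = 4% | 0.80^2 = 64% |

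**What the Cox model then returns.** A Cox model was fitted to k deaths in 28 vs 0 in 14, with deaths spread over Days 5 to 60 and survivors censored at Day 70 (assumed). The fitted hazard ratio runs off to about 10^8 or more with a standard error above 13,000. The Wald p-value is 0.999 for every k from 1 to 12.

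| Deaths | Cox Wald | Cox score | Cox LR | Chi-square | Fisher | Difference (Newcombe 95% CI) |
|---|---|---|---|---|---|---|
| 5/28 vs 0/14 | 0.999 | 0.100 | 0.038 | 0.092 | 0.151 | 17.9% (−5.9 to 35.6) |
| 8/28 vs 0/14 | 0.999 | 0.032 | 0.007 | 0.026 | 0.037 | 28.6% (3.3 to 47.1) |

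The chi-square for 8 vs 0 is 42 × (8 × 14 − 20 × 0)² / (28 × 14 × 8 × 34) = 4.94, p = 0.026. It is only approximate: the expected number of placebo deaths is 8 × 14/42 = 2.7.

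**How often each method picks up an excess.** Simulation at 28:14 with exponential death times, censoring at Day 60, 2,000 trials per row, level 0.05, counting rejections in the harm direction only:

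| Placebo vs AP-SA02 mortality (assumed) | Cox Wald | Cox LR | Log-rank | Chi-square on deaths |
|---|---|---|---|---|
| 5% vs 30% | 2% | 59% | 46% | 49% |
| 5% vs 40% | 15% | 79% | 73% | 77% |
| 10% vs 40% | 17% | 60% | 52% | 57% |

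The Wald weakness goes beyond trials with no placebo death. In the last row, 100 − 23 = 77% of trials have at least one, and Wald rejects in at most 17/77 = 22% of those. Even if the log-rank test rejected in every zero-death trial, it would still reject in at least (52 − 23)/77 = 38% of the rest.

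**The case against.** A reader might infer that mortality is compared only through the Cox model, so that a real excess of deaths on AP-SA02 would be reported as no difference. The documents do not support this. SAP 3.7.1 counts fatal adverse events by arm in the same dosed subjects through EOS, with a chi-square p-value. Protocol 8.2 makes death a serious outcome, and nothing exempts deaths from the infection itself. At 8/28 vs 0/14 that table would show 29% vs 0%. In the simulations, a chi-square on deaths is at least as sensitive as the log-rank test. Death also enters the clinical outcome and the late composite.

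Three further points stand. The near-1 p-value requires a Wald test, which the SAP does not name; a score or likelihood-ratio p-value would behave sensibly. A diverging hazard ratio with an unbounded interval signals that nothing could be estimated, not that the arms are alike. And the zero-death case is uncommon in Phase 2a if placebo mortality is 20% or more.

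They do not remove the gap. The fatal-event table gives no difference and no interval. It covers each phase in the Safety Population, not the Per Protocol MITT or the Persistence and Clearance comparisons; in those sets the Cox model is the only planned comparison of death on its own. Protocol 9.2.1 promises 95% intervals by arm for Phase 2a endpoints, and SAP section 6 does not record dropping them. Because no formal testing is intended, estimates with intervals matter more.

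**Conclusion.** The point holds for the time-to-death endpoint, not for the plan's handling of mortality as a whole. The planned quartiles will be missing in any arm with mortality below 25%. The hazard ratio and CI will be missing whenever an arm has no deaths: for Phase 2a placebo, 49%, 23% or 4% of the time at assumed mortality of 5%, 10% or 20%, and for the planned Phase 1b placebo group of 2, most of the time at any of these rates. A Wald p-value, if used, would then be near 1, would stay weak when placebo has a single death, and could sit in the same report as a chi-square of 0.026 on the same deaths. The sizes rest on assumed mortality rates, the planned 28:14 and 6:2 splits, and near-complete follow-up. This is a cheap improvement, not a flaw that would hide an excess of deaths.

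**What to change.** In SAP 3.4.1, for time to death:

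- Report deaths as n/N by arm, and Kaplan-Meier mortality at Day 12 and EOS with the difference and 95% CI. If follow-up is complete, use an exact or Newcombe interval for the difference. EOS falls on different days for different subjects (Days 39 to 81 in the schedule), so name the day at which the curve is read.
- Add a Kaplan-Meier plot for death, as for the other time-to-event endpoints.
- If a p-value is kept, specify the log-rank (score) test.
- If a hazard ratio is kept, use Firth's penalised likelihood with a profile-likelihood CI, which stays finite when an arm has no deaths.

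The cost is SAP wording, one extra table and one figure. No new data are needed. SAP section 7 says "Analyses will be performed using SAS® version 9.3 or higher", and these methods are options within that software.

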### 3.4.2 Subgroups Analysis

Subgroup analyses will be performed for two endpoints clinical response and microbiological response:

- MRSA subjects
- Blood cultures positive for SA on Day -1 prior to study drug administration (blood cultures are tested by local microbiology laboratories)
- Persistent SAB on 2 blood cultures obtained over 72 hours prior to study drug administration (blood cultures are tested by local microbiology laboratories)
- Source control achieved (e.g., abscess drainage, catheter or intravascular device removal, washout of infected joint, other)
- Foci of infection present at Screening

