4.1 Inclusion Criteria

Inclusion criteria for Phase 1b and 2a

Subjects who meet all of the following criteria will be eligible to participate in the study:

1. Is able and willing to provide written informed consent or have consent provided by an LAR;
2. Is a hospitalized male or female adult subject aged 18 years or older at time of consent;
3. Has SAB identified from at least 1 blood culture or from a rapid diagnostic test within 72 hours of randomization. Time of positive blood culture starts from when specimen is collected for blood culture;
4. Has a plan for source control within 3 days after randomization to be completed within 7 days of randomization if relevant (eg, abscess drainage, washout or debridement of infected material) or has source already controlled;
5. If an FCBP, the subject must agree to use a highly effective method of birth control (defined as those, alone or in combination, that result in a low failure rate [ie, less than 1% per year]) from Day 1 through 60 days following the last dose of study drug;

Note: FCBP must have a negative serum pregnancy test within 72 hours prior to randomization. An FCBP is any female, regardless of sexual orientation, who meets the following criteria: has not undergone a hysterectomy or bilateral oophorectomy, or has not been naturally postmenopausal for at least 12 consecutive months (ie, has had menses at any time in the preceding 12 consecutive months).

6. If a male subject, the subject must agree to use barrier contraception (ie, condoms) from Day 1 through 60 days following the last dose of study drug;

Additional inclusion criteria for Phase 2a only

7. Has at least 1 of the following signs/symptoms at or within 72 hours prior to randomization:
 - a. Documented temperature $\geq 38.0^{\circ}\text{C}$ (100.4°F) or $\leq 36.0^{\circ}\text{C}$ (96.8°F) measured orally, $\geq 38.5^{\circ}\text{C}$ (101.3°F) or $\leq 36.5^{\circ}\text{C}$ (97.7°F) measured tympanically, or $\geq 39^{\circ}\text{C}$ (102.2°F) or $\leq 37^{\circ}\text{C}$ (98.6°F) measured rectally;
 - b. Heart rate >90 beats per minute;
 - c. Respiratory rate >20 breaths per minute;
 - d. White blood cell count $\geq 12.0 \times 10^9$ cells/L or $\leq 0.4 \times 10^9$ cells/L, or $\geq 10\%$ immature neutrophils;
 - e. Systolic blood pressure <90 mmHg; and/or
 - f. Pain associated with focal site of infection.

8. Has at least 1 of the following:

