9.2 Statistical Methods

Predefined or post-hoc statistical analysis for all subjects may be performed to compare the treatment groups that are randomized based on the following:

- MRSA subjects (subgroup will be for Phase 2a only);
- Blood cultures positive for SA on Day -1 prior to study drug administration; and
- Source control achieved (eg, abscess drainage, catheter or intravascular device removal, washout of infected joint).

Note: The final SAP will finalize the subgroup analyses.

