### 3.3.4 Demographic and Baseline Characteristics

Demographics and baseline characteristics will be summarized descriptively by Phase and treatment based on the randomized subjects.

The following demographic and baseline characteristics will be summarized:

- Age (Years)
- Age categories (<65 Years, ≥65 Years)
- Sex (Male, Female)
- Race (American Indian or Alaska Native, Asian, Black or African American, Native Hawaiian or Other Pacific Islander, White, Other)
- Ethnicity (Hispanic or Latino, Not Hispanic or Latino, Not Reported, Unknown)
- Height (cm)
- Weight (kg)
- Body mass index (kg/m^2)
- Modified Duke criteria (Major: Positive blood cultures for IE, Evidence of endocardial involvement; Minor: Predisposition, Fever, Vascular phenomena, Immunologic phenomena, Microbiologic evidence)
- Blood cultures positive for SA on Day -1 prior to study drug administration based on blood cultures tested by local microbiology laboratories
- Persistent SAB on 2 blood cultures obtained over 72 hours prior to study drug administration based on blood cultures tested by local microbiology laboratories
- Type of baseline SA from blood culture isolates based on blood cultures tested by local microbiology laboratories
  - MRSA
  - Methicillin-susceptible SA (MSSA)

- Unknown
- Randomized based on rapid testing (Yes, No)
- Signs/symptoms for focal site of SA infection (Pain at site of infection, Joint pain, Redness, etc.)
- Foci of SA infection at Screening (Head, Neck, Spine, Chest, etc.)
- Source control (Abscess drainage, Catheter or intravascular device removal, Washout of infected joint, Other)
- Adequacy of source control achieved by physician (Yes, No)
- Signs and symptoms of SAB at Screening (per protocol [section 7.3 of protocol](#))
  - Documented temperature  $\geq 38.0^{\circ}\text{C}$  ( $100.4^{\circ}\text{F}$ ) or  $\leq 36.0^{\circ}\text{C}$  ( $96.8^{\circ}\text{F}$ ) measured orally,  $\geq 38.5^{\circ}\text{C}$  ( $101.3^{\circ}\text{F}$ ) or  $\leq 36.5^{\circ}\text{C}$  ( $97.7^{\circ}\text{F}$ ) measured tympanically, or  $\geq 39^{\circ}\text{C}$  ( $102.2^{\circ}\text{F}$ ) or  $\leq 37^{\circ}\text{C}$  ( $98.6^{\circ}\text{F}$ ) measured rectally
  - Heart rate  $>90$  beats per minute
  - Respiratory rate  $>20$  breaths per minute
  - White blood cell count  $\geq 12.0 \times 10^9$  cells/L or  $\leq 0.4 \times 10^9$  cells/L, or  $\geq 10\%$  immature neutrophils
  - Systolic blood pressure  $<90$  mmHg; and/or

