- v. Investigator will provide an assessment of whether additional imaging is needed for potential metastatic infection based on clinical signs/symptoms of SA infection.
- w. All subjects with an intravascular catheter present at admission that is not thought to be infected and is not planned on being removed within 3 days of randomization should receive an ultrasound to evaluate for the presence of an intravascular clot within 2 days of randomization unless this was done within 7 days prior to Screening.

x. All subjects will receive a TTE and/or TEE ECHO within 3 days of randomization unless this was done within 7 days prior to Screening. Subjects with endocarditis should have a follow-up TTE or TEE between Days 7 and 14. All effort should be made to perform this before administration of study drug.

y. All work-up for distant sites of metastatic infection and all decisions regarding source control procedures will be performed as per primary team. IV catheters known or suspected to be infected must be removed or changed as soon as possible within 72 hours after randomization. Sites should identify source control within 3 days; potential source or evidence of ongoing infection after 7 days may be considered a clinical failure.

z. AKI will be defined as stage 1 or higher using modified RIFLE criteria at any time within the first 7 days or new need for renal replacement therapy between Day 1 and EOS

aa. Serum for AP-SA02 anti-phage antibodies will be performed prior to the first dose.

bb. HIV antibody, HBsAg, and HCV antibody testing will be performed at Screening, only if status is unknown.

cc. FCBPs only must have a negative serum pregnancy test within 72 hours prior to randomization. Results can be from a local laboratory and will be confirmed at the central laboratory.

dd. A 12-lead ECG will be performed post first dose of the day.

ee. Assessments include chemistries, hematology, coagulation, CRP, and procalcitonin. See [Appendix B of protocol](#) for a list of clinical laboratory analytes.

ff. Clinical laboratory assessments and IL-10 will be performed post-dose after the second infusion.

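### The SAP's source-control subgroup has no time cut-off, so it can be defined by an event after first dose and its treatment comparison may be biased

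*SAP*

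**What the plan says.** SAP 3.4.2 states: "Subgroup analyses will be performed for two endpoints clinical response and microbiological response". One of the five listed factors is "Source control achieved (e.g., abscess drainage, catheter or intravascular device removal, washout of infected joint, other". No date, visit or reference to first dose is attached to it.

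Two other places bear on when source control happens and how it is classified:

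- Protocol 4.1, inclusion criterion 4, admits a subject who "Has a plan for source control within 3 days after randomization to be completed within 7 days of randomization if relevant", or who "or has source already controlled". The factor therefore mixes subjects controlled before randomisation with subjects for whom control is only planned.
- SAP 3.3.4 lists the type of source control, and also "Adequacy of source control achieved by physician (Yes, No", among demographic and baseline characteristics. SAP 3.1.2 defines baseline as the last available value before the first dose of study drug.

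Footnote y of the Schedule of Procedures (Appendix A of both documents) leaves source-control decisions to the primary team and adds that "potential source or evidence of ongoing infection after 7 days may be considered a clinical failure".

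**The concern.** A subgroup comparison keeps the protection of randomisation only if membership is fixed before treatment can affect it. Here membership can be settled up to a week after randomisation. A subject has to survive and remain treatable long enough to have the procedure, and the primary team may decide for or against it in the light of the clinical course. An early death before the procedure would leave the subject outside the achieved group, and death is also a non-response in protocol Table 2.

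Footnote y adds a direct link. A source still present after 7 days may itself contribute to clinical failure, and clinical response is one of the two subgroup endpoints. Selecting on source control may then partly select on the outcome.

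At stake is whether a difference seen in subjects with source control can be read as a treatment effect in a recognisable patient group. A baseline table that includes post-dose source control could also show an arm imbalance that treatment helped to produce.

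**Working it through.** The documents give no size, power or expected effect for this subgroup, so there is no plan figure to reproduce. The check sets out the timing first and then gives an illustration with assumed inputs.

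**Timing**

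- Randomisation and first dose are on Day 1; planned dosing runs to Day 5 (protocol Appendix A).
- Criterion 4 allows completion within 7 days of randomisation. Counting from Day 1, that reaches Day 1 + 7 = Day 8, which is 8 - 5 = 3 days after the last planned dosing day.
- Baseline closes at first dose (SAP 3.1.2).
- SAP 3.4.1 determines microbiological outcome at Day 5 and Day 7 as well as later, and analyses clinical response from Day 12. A Day 5 or Day 7 microbiological outcome can therefore be known before source control is complete.

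Take a subject whose drainage is planned and done on Day 4. Classified by status before first dose, the subject is a No; classified by status at any time in the study, a Yes. SAP 3.4.2 fits either. It also does not say where a subject with no source needing control belongs, although criterion 4 applies the plan only if relevant.

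The other factors in SAP 3.4.2 do not share the problem. Day -1 cultures, persistent bacteremia and "Foci of infection present at Screening" are anchored before dosing, and MRSA is a property of the isolate.

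**Illustration 1: treatment changes source control (all inputs assumed)**

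Half the subjects have good prognosis. Response is 50% in good and 10% in poor prognosis, in both arms, so the drug has no direct effect. Overall response is 0.5 × 0.5 + 0.5 × 0.1 = 30% in each arm, a true difference of 0. In the control arm source control is achieved in 90% (good) and 50% (poor).

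With *g* and *p* the proportions achieving source control in good and poor prognosis, response within the achieved subgroup is

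R(g, p) = (0.5·g·0.5 + 0.5·p·0.1) / (0.5·g + 0.5·p)

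Control: R(0.9, 0.5) = 0.250/0.70 = 35.7%.

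| Treated arm, poor prognosis | R | Apparent difference (points) |
|---|---|---|
| 50% (no change) | 0.250/0.70 = 35.7% | 0 |
| 60% | 0.255/0.75 = 34.0% | -1.7 |
| 80% | 0.265/0.85 = 31.2% | -4.5 |
| 40% | 0.245/0.65 = 37.7% | +2.0 |
| 20% | 0.235/0.55 = 42.7% | +7.0 |

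**Illustration 2: source control depends on eventual response, equally in both arms (all inputs assumed)**

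If source control is achieved in a fraction *a* of responders and *b* of non-responders, a response rate *r* becomes r′ = r·a / (r·a + (1 - r)·b). Take *a* = 0.3 and *b* = 0.9, with true rates of 60% and 30%:

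- Treated: 0.18/0.54 = 33.3%
- Control: 0.09/0.72 = 12.5%
- Difference: 20.8 points instead of 30

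The odds are multiplied by *a*/*b* in both arms, so the odds ratio stays at (0.6/0.4)/(0.3/0.7) = 3.5. If the true rates are equal, the difference stays 0. This mechanism changes an absolute difference but does not create one.

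**The case against.** The strongest reply is that the factor is already a baseline one. SAP 3.3.4 places source control among baseline characteristics, SAP 3.1.2 closes baseline at first dose, and both schedules mark source control at Day 1 only. The 7-day window sits in an eligibility criterion about a plan, not in the subgroup definition. That reading is possible, but SAP 3.4.2 does not state it. Footnote y to the same Day 1 entry allows action after randomisation, and adequacy of achieved control cannot be settled before first dose for a subject whose procedure is only planned. The ambiguity remains.

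The second reply is that bias has not been shown. The trial is blinded to subjects, sites, investigators and sponsor, and source-control decisions lie with the primary team. If treatment and early outcome do not alter source control, Illustration 1 gives zero, and Illustration 2 cannot produce a false effect. This stands, and limits the conclusion to possible bias. Blinding does not remove the route entirely, because a treatment effect on the clinical course could still lead to different decisions.

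A reader might also infer that the section reports one level only, or lacks needed safeguards because it has no exploratory label or interaction estimate. The text does not carry that far. Foci of infection has several levels, adequacy is collected as Yes/No, nothing forbids reporting the complement, SAP 3.1.4 says there will be no formal testing, and protocol 9.2 makes such analyses optional. These are matters of missing detail or preference.

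**Conclusion.** The point holds as a definitional gap with a possible bias. SAP 3.4.2 sets no time anchor, criterion 4 lets the defining event fall after first dose, and footnote y ties that event to clinical failure. Calling post-dose source control a baseline characteristic in SAP 3.3.4 conflicts with SAP 3.1.2.

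The size cannot be derived from the documents. The range of -4.5 to +7.0 points rests entirely on the assumed prognosis mix, response rates and source-control rates in Illustration 1, and becomes 0 if treatment does not change source control.

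Two stronger conclusions might be drawn and are not supported. One is that the subgroup effects are biased: that needs treatment or early outcome to affect source control, which the documents do not establish. The other is that the subgroup would rest on 8 treated and 4 placebo subjects. Those numbers (SAP 2.2.4) are the enrolment minimum for Phase 2a MRSA subjects. They are not the size of the source-control subgroup, and MRSA status is a randomisation stratum without this timing problem.

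**What to change.** Before database lock, amend SAP 3.4.2 and 3.3.4 to use one factor: *source controlled, or no source needing control, before first dose: yes/no*, derived from recorded source-control dates. Report both levels, each with the treatment difference and its 95% CI. Report source control completed after first dose separately by arm, as a post-baseline outcome, and take it out of the baseline table.

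The cost is SAP wording and a few table rows; no enrolment, treatment or clinical procedure changes. There are two limits. The yes level will be smaller than under an any-time definition, so its estimate will be less precise. The derivation also needs source-control dates in the eCRF; the documents do not show whether they are collected, so this should be checked first.
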